1.3. Schedule of Activities (SoA)

	Screen	Lead in Period -11 to -1	Treatment Period												Safety Follow-up	ET
			Titration Period Days 0 to 35											Maintenance Days 36 to 46		
Day	-21 to -12	-11	0	3	7	10	14	17	21	24	28	31	35	46	53	ET
Visit Window (days)	0	+/-3	+3	-1/+2	-1/+2	-1/+2	-1/+2	-1/+2	-1/+2	-1/+2	-1/+2	-1/+2	-1/+2	+3	+/-3	
Visit	1	2	3	4	5	6	7	8	9	10	11	12	13	14	801	ET
Telephone visits are indicated by shaded columns. Telephone visits can become office visits. Site documentation will serve as the source for telephone visits.																
Informed Consent Signed	X															
Participant eligibility review	X	X														
IWRS	X	X	X	X	X	X	X	X	X	X	X	X	X	X	X	
Clinical Assessments																
Participant demographics	X															
Medical history and preexisting conditions	X															
Physical exam. /height	X															
Body Weight	X		X				X				X			X		X
Note: Participants should be advised to remove their shoes/coats and empty their pockets before the body weight is obtained.																

	Screen	Lead in Period -11 to -1	Treatment Period												Safety Follow-up	ET
			Titration Period Days 0 to 35											Maintenance Days 36 to 46		
Day	-21 to -12	-11	0	3	7	10	14	17	21	24	28	31	35	46	53	ET
Visit Window (days)	0	+/-3	+3	-1/+2	-1/+2	-1/+2	-1/+2	-1/+2	-1/+2	-1/+2	-1/+2	-1/+2	-1/+2	+3	+/-3	
Visit	1	2	3	4	5	6	7	8	9	10	11	12	13	14	801	ET
Vital signs blood pressure and heart rate	X		X				X				X			X		X
	Note: Vital sign measurements should be determined after participants have been seated quietly for at least 5 minutes in a chair with feet on the floor. The arm used for blood pressure measurement should be supported at heart level															
ECG (12-lead, local)	X															
	Participants must be supine for approximately 5 to 10 minutes before ECG collection and remain supine, but awake, during ECG collection.															
Concomitant medications	X	X	X	X	X	X	X	X	X	X	X	X	X	X	X	X
Adverse events and product complaints	X	X	X	X	X	X	X	X	X	X	X	X	X	X	X	X

	Screen	Lead in Period -11 to -1	Treatment Period												Safety Follow-up	ET
			Titration Period Days 0 to 35											Maintenance Days 36 to 46		
Day	-21 to -12	-11	0	3	7	10	14	17	21	24	28	31	35	46	53	ET
Visit Window (days)	0	+/-3	+3	-1/+2	-1/+2	-1/+2	-1/+2	-1/+2	-1/+2	-1/+2	-1/+2	-1/+2	-1/+2	+3	+/-3	
Visit	1	2	3	4	5	6	7	8	9	10	11	12	13	14	801	ET
Participant Education and Management																
Diabetes education and nutrition counseling		X														

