Participants who discontinue investigational product (IP) permanently before completion of the treatment period for any reason will also be discontinued from the study. An (ET) visit should be conducted as soon as reasonably possible. After the ET visit, a safety follow-up assessment (Visit 801) should be conducted approximately 1 week after the ET Visit.

Transcribing Data into the eCRF at the ET Visit

At the early termination visit, the investigator should transcribe the following data from the day before visit into the eCRF:

- ICR
- ISF
- DIA
- LY900014 dose

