8.2.2. Vital Signs

For each participant, vital signs measurements should be conducted according to the Schedule of Activities (Section 1.3).

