All CGM outcome variables will only be derived for Visit 3 (baseline) and Visit 14 (endpoint) based upon the CGM data collected from valid CGM days, excluding data (if any) that are collected while patients are temporarily off IP. A valid CGM day to be counted into the calculation for a visit must have at least 70% of the total measures that are supposed to be obtained.

For laboratory values, both conventional (CN) and Systeme International (SI) units will be presented. Therefore, both % and mmol/mol will be presented for HbA1c and both mg/dL and mmol/L will be presented for glucose measurements.

Table ITSZ.6.2. Baseline and Post-Baseline Definitions and Patient Population by Study Period and Type of Analysis

Baseline and Post-Baseline Definitions and Patient Population by Study Period and Type of Analysis			
Study Period/Analysis	Patient Population	Baseline Observations	Post-Baseline Observations
Lead-In Period			
AEs	Enrolled Population	Prior to first dose of open-label Humalog (or Visit 2 date if the dose date is missing)	The entire lead-in period after first dose of open-label Humalog and prior to first dose of IP (or Visit 3 date if the dose date is missing)
Treatment Period (including Titration and Maintenance periods) and Safety Follow-Up Visit where applicable			
TEAEs	All patients in the Treated Population	Prior to first dose of IP (or Visit 3 if the dose date is missing)	From first dose of IP to last dose of IP AND From first dose of IP to Visit 801
Weight and vital signs	All patients in the Treated Population with a baseline and a post-baseline observation	Last of Visits 1 and 3	Visits 7, 11, 14 while on IP AND Visits 7, 11, 14 and 801 regardless of IP use
Basal, bolus, and total insulin doses, and bolus/total insulin dose ratios continuous analysis ^a	All Randomized Patients	Visits 3	Visit 14
ICR, ISF, and DIA	All patients in the Treated Population with a baseline and at least one post-baseline observation	Last value of Visits 2-3 prior to or on the date of the first dose of IP	Visit 4-14 while on IP

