6.10.5. Vital Signs and Other Physical Findings

Post-baseline measurements and change from baseline to post-baseline for vital signs (systolic blood pressure [SBP], diastolic blood pressure [DBP], pulse rate) and physical characteristics (weight, BMI) at the scheduled visits will be summarized for patients who have both baseline and at least 1 post-baseline result.

The measurements during the treatment period will be analyzed by MMRM model similar to that for the primary endpoint, i.e., with baseline value of the response variable, visit as fixed factors and patient as the random factor.

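### SAP Table ITSZ.6.2 takes weight and vital signs at Visit 801, where none are scheduled, and omits the early termination visit, where they are

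*SAP*

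**What the plan says.** **Where the data are collected.** In the Schedule of Activities (protocol 1.3), the row "Vital signs blood pressure and heart rate" and the body weight row are marked at Visits 1, 3, 7, 11, 14 and ET. The Visit 801 cell is blank in both. Protocol 8.2.2 adds no further time point: "vital signs measurements should be conducted according to the Schedule of Activities (Section 1.3").

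**What happens to early stoppers.** Participants who stop IP permanently also leave the study. Protocol 4.1.1 says of them: "An (ET) visit should be conducted as soon as reasonably possible". It continues: "After the ET visit, a safety follow-up assessment (Visit 801) should be conducted approximately 1 week after the ET Visit".

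**What the SAP analyses.** Table ITSZ.6.2 gives two post-baseline sets for weight and vital signs: "Visits 7, 11, 14 while on IP" and "Visits 7, 11, 14 and 801 regardless of IP use". The population for the row is "All patients in the Treated Population with a baseline and a post-baseline observation". SAP 6.10.5 describes the summary in matching terms: results "at the scheduled visits will be summarized for patients who have both baseline and at least 1 post-baseline result". The measurements are then modelled by MMRM, which under SAP 6.1 takes observations at scheduled post-baseline visits.

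**What SAP 6.1 says about periods.** The text above the table defines a treatment period (first dose to Visit 14) and a combined treatment and follow-up period (first dose to Visit 801). Each has a version that takes in all data whether or not IP was in use. SAP 6.1 also counts an office-visit measurement as on IP if the visit falls within 14 days of the last dose.

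**The concern.** The visit list in the table does not match the visits at which the data exist. For someone who stops early, the last weight, blood pressure and heart rate are taken at ET. Followed literally, the table gives those values no way into either set, even when the ET visit is close enough to the last dose to count as on IP. Visit 801, the one visit that the wider set adds, has no scheduled measurement to contribute.

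The participants concerned are those who did not complete treatment. One who stops before Visit 7 (Day 14) has ET as the only scheduled post-baseline measurement. That person would fail the row's requirement for a post-baseline observation and be missing from the weight and vital-signs summary.

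**Working it through.** **1. Visit comparison.** The schedule has 16 visit columns: Visits 1 to 14, 801 and ET. The concomitant medication and adverse event rows are marked in all 16, so 801 and ET are separate columns and the blank at 801 is not an effect of table layout. The body weight and vital signs rows give the same pattern.

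| Source | Post-baseline visits |
|---|---|
| Protocol 1.3, measurement scheduled | 7, 11, 14, ET |
| SAP Table ITSZ.6.2, on-IP set | 7, 11, 14 |
| SAP Table ITSZ.6.2, set regardless of IP use | 7, 11, 14, 801 |

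The wider set has one visit without scheduled data (801) and lacks one with data (ET).

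**2. Does another part of the plan repair this?** No. SAP 6.10.5 and the MMRM description both speak of scheduled visits, and no section maps an ET value to a visit. The SAP period definitions would include ET values, but the table, which sets the observations for each analysis, does not list them. The SAP was written to protocol amendment (a). Neither that amendment's log nor the visible summary of the later changes mentions weight or vital signs, so a version difference is not shown to explain the mismatch.

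**3. How many participants.** Inputs from SAP 5.2 and protocol 9.2: 30 evaluable completers, 10% dropout, about 34 assigned.

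- The plan's own figure: 30 / (1 − 0.10) = 33.3, rounded up to 34. It reproduces.
- Expected early stoppers: 0.10 × 34 = 3.4; the difference between assigned and evaluable is 34 − 30 = 4. So 3 to 4.
- Stops before Visit 7, assuming that dropouts spread evenly over the 46 treatment days: 3.4 × 14 / 46 = 1.03, about 1.

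The even spread is an assumption; the documents give no timing for dropout.

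**4. Can an ET value simply go to the nearest visit?** Visits 7, 11 and 14 fall on Days 14, 28 and 46.

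- ET on Day 18 is 4 days from Visit 7 and 10 from Visit 11. The nearest is Visit 7, which should already hold a value.
- ET on Day 32 is 4 days from Visit 11 and 14 from Visit 14. The nearest is Visit 11, which should already hold a value.

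A nearest-visit rule therefore collides with existing data. A rule that uses the next scheduled visit without a value sends these two to Visits 11 and 14, with no collision.

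**The case against.** The best defence is that no sentence in the SAP discards ET values. The period definitions in 6.1 include all data from first dose, and ET falls inside them. This stands to the extent that a reader should not infer a decision to exclude ET. What the documents show is a table that does not admit the values and a period definition that does.

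Second, the table names ET in no row. ICR, ISF and DIA are also transcribed at ET (SAP 6.9.2 and 6.9.3), yet their row runs only from Visit 4 to Visit 14. So the lack of an ET rule is general. That is true, but the weight and vital-signs row goes further, because it names a visit with no scheduled measurement.

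Third, naming 801 biases nothing, and the block heading qualifies the follow-up visit as included where applicable. That stands: this half is a clean-up. It would also be too strong to say that the wider set can never add anything. A temporary interruption of IP, or an inadvertently enrolled participant who continues off IP (protocol 7.2.1), could supply off-IP values at Visits 7 to 14.

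Fourth, leaving an untimed ET value out of a by-visit MMRM is defensible. SAP 6.3 relies on missing at random, and those who stop after Visit 7 or 11 keep their earlier values. This stands for the model. It does not help the descriptive summary, where a participant with only an ET value is absent.

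**Conclusion.** Wrong as written; severity minor. The row disagrees with the schedule on two visits, and the SAP contradicts itself on whether ET values belong in the analysis.

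The 3 to 4 participants are an upper figure and not an expected loss. The 10% is a planning assumption. ET is held only if possible (protocol 7.1), participants lost to follow-up may have no ET visit, and the protocol expects discontinuation to be uncommon. The figure of about 1 with no value in the summary rests on the even-spread assumption above.

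A reader might infer that early stoppers vanish from the safety report. The documents do not support that. Those participants remain in the adverse event, serious adverse event and discontinuation tables (SAP 6.10.2), and they receive a narrative if they stopped because of an adverse event (SAP 6.10.6). A vital-sign change that the investigator judges clinically significant is itself an adverse event (protocol 10.3.1). Nor do the documents say that the stops would be for safety reasons. Vital signs sit among the tertiary and exploratory endpoints, and the primary endpoint and sample size are untouched.

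**What to change.** In Table ITSZ.6.2, weight and vital signs row, and in SAP 6.10.5:

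1. Replace 801 with ET in the set regardless of IP use.
2. Admit an ET value to the on-IP set when it meets the existing 14-day rule.
3. Add a descriptive line for the last post-baseline value, including ET, so that early stoppers are counted.
4. In the by-visit MMRM, use an ET value only for the next scheduled visit (7, 11 or 14) that has no value. Do not use the nearest visit, which may already hold one.

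Item 4 labels some values with a later nominal day than the day they were taken, by up to one visit interval (28 − 14 = 14 days, or 46 − 28 = 18 days). The SAP should say so. Item 3 carries no such approximation.

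The cost is SAP wording and a small programming change. The ET measurements are already scheduled, so no protocol procedure changes.

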6.2. Adjustments for Covariates

The MMRM model for the analysis of the primary efficacy endpoint will include the fixed class effect of visit, and the random effect of patient, as noted in Sections 6.9.

The ANCOVA model will include baseline as a covariate, as noted in Sections 6.9 to 6.10.

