9.4.1. General Considerations

Unless otherwise specified, all efficacy and safety analyses will be conducted on the Treated Population. Unless otherwise noted, all tests will be conducted at a 2-sided alpha level of 0.05, and confidence intervals will be calculated at 95%, 2-sided. Comparison between baseline and

endpoints will be performed at the full significance level of 0.05. No multiplicity adjustment will be made. Baseline is defined as the last non-missing measurement at or before the treatment assignment (Visit 3) unless otherwise specified.

An analysis of covariance (ANCOVA) will be used to analyze continuous variables that are planned to be collected only for baseline and endpoint. The model will include baseline as a covariate.

A restricted-maximum-likelihood-based, mixed model repeated measures (MMRM) analysis will be used to analyze continuous longitudinal variables collected only at baseline and more than one scheduled post-baseline visits according to SoA in Section 1.3. All the longitudinal observations at each scheduled post-baseline visit will be included in the analysis. The model for the analysis of the primary efficacy endpoint will include the fixed class effect of visit, and the random effect of patient. An unstructured covariance structure will be used to model the within-patient errors. Significance tests will be based on least-squares (LS) means and Type III tests. SAS PROC MIXED will be used to perform the analysis. If this analysis fails to converge, the following covariance structures will be tested in order:

- Toeplitz with heterogeneity
- Autoregressive with heterogeneity
- Compound symmetry with heterogeneous variances
- Toeplitz
- Autoregressive
- Compound symmetry without heterogeneous variances

The first covariance structure that converges will be used. The Kenward-Roger approximation will be used to estimate denominator degrees of freedom. If the analysis still does not converge with Compound symmetry without heterogeneous variances, only summary statistics will be provided.

For continuous measures, summary statistics will include sample size, mean, standard deviation, median, minimum, and maximum for both the actual and the change from baseline measurements. Least-square (LS) means and standard errors derived from the analysis models will also be displayed for the actual and the change from baseline measurements.

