9.4.2. Primary Endpoint(s)

The primary objective of this study is to evaluate the percentage of time with glucose values within target range (70 to 180 mg/dL, both inclusive) after 35 days of using the study titration

scheme with LY900014 treatment and degludec. Both actual and change from baseline will be derived and analyzed by the ANCOVA model as described in Section 9.4.1.

The primary analyses will be conducted based upon the CGM data collected for Visit 3 (baseline) and Visit 14 (endpoint), excluding data (if any) that are collected while patients are temporarily off Humalog during the lead-in period or temporarily off IP during the maintenance period.

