- for data collected as running records with an exact date such as adverse events (AEs) where the date of the measures is not tied with the date of an office visit, postbaseline

data with date \leq (last study drug dose date) will be considered as data on IP for the treatment period.

An analysis of covariance (ANCOVA) will be used to analyze continuous variables that are planned to be collected only for baseline and endpoint. The model will include baseline as a covariate.

A restricted maximum likelihood based, mixed model repeated measures (MMRM) analysis will be used to analyze continuous longitudinal variables collected only at baseline and more than one scheduled post-baseline visits according to SoA in Section 1.3. All the longitudinal observations at each scheduled post-baseline visit will be included in the analysis. The model for the analysis of the primary efficacy endpoint will include the fixed class effect of visit, and the random effect of patient. An unstructured covariance structure will be used to model the within patient errors. Significance tests will be based on least squares (LS) means and Type III tests. SAS PROC MIXED will be used to perform the analysis. If this analysis fails to converge, the following covariance structures will be tested in order:

- Toeplitz with heterogeneity
- Autoregressive with heterogeneity
- Compound symmetry with heterogeneous variances
- Toeplitz
- Autoregressive
- Compound symmetry without heterogeneous variances

The first covariance structure that converges will be used. The Kenward Roger approximation will be used to estimate denominator degrees of freedom. If the analysis still does not converge with Compound symmetry without heterogeneous variances, only summary statistics will be provided.

For continuous measures, summary statistics will include sample size, mean, standard deviation, median, minimum, and maximum for both the actual and the change from baseline measurements. Least square (LS) means and standard errors derived from the analysis models will also be displayed for the actual and the change from baseline measurements.

For categorical measures, summary statistics will include sample size, frequency, and percentages. No statistical analyses will be conducted for baseline and endpoint comparison.

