6.9. Efficacy Analyses

6.9.1. Primary Outcome and Methodology

The primary objective of this study is to evaluate the percentage of time with glucose values within target range (70 to 180 mg/dL, both inclusive) after 35 days of using the study titration scheme with LY900014 treatment and degludec. Both actual and change from baseline will be derived and analyzed by the ANCOVA model as described in Section 6.1.

The primary analyses will be conducted on the Treated Population based upon the CGM data collected for Visit 3 (baseline) and Visit 14 (endpoint), excluding data (if any) that are collected while patients are temporarily off Humalog during the lead-in period or temporarily off IP during the maintenance period. Comparison between baseline and endpoints will be performed at the full significance level of 0.05.

Derivation and analysis of primary endpoint (derived for 24-hour, daytime and nighttime and by-meal) and other CGM endpoints are described in Section 6.13.

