6.9.2. Other Secondary Efficacy Analyses

The analyses described in Section 6.9.2 will include data collected from the Treated Population. Details for the CGM analyses are described in Section 6.13. Continuous secondary efficacy variables, as well as the change from baseline for these variables, will be analyzed by the MMRM or ANCOVA model as described in Section 6.1.

The ICR data from the day before a scheduled visit will be transcribed in eCRF at Visit 2, Visit 3 through Visit 14 and ET Visit, respectively. Any changes and associated to meals for ICR during the Treatment period will be captured. A listing will be provided to include ICR data collected at Visit 2, changes in ICR by meal captured during Treatment period in the eCRF. An MMRM model similar to that for the primary endpoint will be used to analyze actual and change from baseline in ICR.

For the following secondary efficacy endpoints data collected for Visit 3 (baseline) and Visit 14 (endpoint), an ANCOVA model as described in Section 6.1 will be used:

- actual and change from baseline in insulin doses, including mean total daily basal (U/day, U/kg/day), mean total daily bolus (U/day, U/kg/day), and mean total daily insulin dose (U/day, U/kg/day) and mean total daily bolus / total daily insulin dose ratios (%)

The investigator will transcribe the Humalog dose at Visit 3 (data from Day -10 to Day -1) and LY900014 dose at Visit 14 (data from Day 36 to Day 45) to eCRF. To assess the insulin doses over the course of 10 days for each visit, the mean total daily basal dose will be derived based on CGM data collected during lead in period (data from Day -10 to Day -1) and maintenance period (data from Day 36 to Day 45), and mean total bolus doses will be derived based upon the eCRF data collected at Visit 3 and Visit 14.

Relationships between ICR and TDD will be evaluated through regression lines (ICR versus 1/TDD) and compared with the “500 Rule,” which is currently used in clinical practice where

ICR = 500/TDD (Section 2.1 in study protocol) by visit. Regression lines with and without intercept will be analyzed. The analyses will be conducted based upon ICR and mean total daily insulin dose (U/day) collected for Visit 3 and Visit 14, separately.

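### SAP 6.1, SAP 6.2 and Protocol 9.4.1 still give the primary endpoint an MMRM where ANCOVA is evidently intended, and the ICR, ISF, DIA and vital-sign models inherit a contradictory definition from it

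*SAP*

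**What the plan says.** **Text that gives the primary endpoint ANCOVA.**
- SAP 6.9.1: "Both actual and change from baseline will be derived and analyzed by the ANCOVA model as described in Section 6.1". Protocol 9.4.2 agrees: "Both actual and change from baseline will be derived and analyzed by the ANCOVA model as described in Section 9.4.1".
- SAP 6.2 supplies the covariate: "The ANCOVA model will include baseline as a covariate, as noted in Sections 6.9 to 6.10".
- SAP 6.1 allocates models by rule: ANCOVA for variables collected only at baseline and endpoint, MMRM for variables with more than one scheduled post-baseline visit. It also says that CGM outcomes are derived only for Visits 3 and 14.
- SAP 6.3 names a completers-only ANCOVA for CGM variables, and SAP 6.13 applies ANCOVA to the continuous CGM variables.

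**Text that gives the primary endpoint an MMRM.**
- SAP 6.1, in the MMRM paragraph: "The model for the analysis of the primary efficacy endpoint will include the fixed class effect of visit, and the random effect of patient". Baseline is not listed.
- SAP 6.2 names the model outright: "The MMRM model for the analysis of the primary efficacy endpoint will include the fixed class effect of visit". It adds patient as random effect, lists no baseline term, and refers to Section 6.9 for it.
- Protocol 9.4.1: "The model for the analysis of the primary efficacy endpoint will include the fixed class effect of visit".

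**Text that borrows that MMRM.**
- SAP 6.9.2: "An MMRM model similar to that for the primary endpoint will be used to analyze actual and change from baseline in ICR". SAP 6.9.3 does the same for ISF and DIA.
- SAP 6.10.5, for vital signs, weight and BMI: "analyzed by MMRM model similar to that for the primary endpoint, i.e., with baseline value of the response variable", then visit as a fixed factor and patient as random.

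**The concern.** Two models are attached by name to one endpoint, in current text, and the comparison with baseline is tested at the full 0.05 level. If the models gave the same answer this would be purely editorial. In the no-baseline form they do not: the point estimate on completers is the same, but the standard error differs whenever baseline is correlated with change.

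The second problem reaches further. The ICR, ISF, DIA and vital-sign analyses are defined only by likeness to the primary-endpoint MMRM. SAP 6.9.1 contains no such MMRM. The places that do describe it disagree on whether baseline is in the model: absent in 6.1 and 6.2, present in 6.10.5. ICR at the end of the maintenance period is a secondary endpoint, so a programmer working from the SAP cannot tell which model produces its LS means and standard errors.

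**Working it through.** **Inputs.** From SAP 5.2 and Protocol 9.2: 30 evaluable participants of 34 assigned, 10% dropout, SD 12 (read as the SD of the change), about 80% probability that the 95% CI half-width is within 4.93 points. From SAP 6.1: two-sided 0.05. Not in the documents, and therefore assumed: baseline-endpoint correlation r = 0.3, 0.5 or 0.7, and equal variances at the two visits.

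**The plan's own figures.** 30/0.90 = 33.3, rounded up to 34. The 80th percentile of the half-width of a one-sample t interval is

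12 × √(χ²(0.80; 29)/29) × t(0.975; 29)/√30 = 12 × √(35.14/29) × 2.045/5.477 = 4.93.

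The probability of a half-width within 4.93 is 0.799. Both figures reproduce. They describe the unadjusted mean change, so the precision statement matches a paired interval rather than the ANCOVA.

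**The MMRM without baseline (SAP 6.1, 6.2).** With change as response there is one post-baseline visit, so the visit factor has one level and the model is a one-sample t-test. With both visits as responses in completers it is a paired t-test. Either way SE = 12/√30 = 2.191 on 29 df. A REML fit with fixed visit and random patient on complete two-visit data gave 2.191.

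**The ANCOVA (SAP 6.9.1).** The LS mean change at the sample mean baseline has the same point estimate. Under equal variances the baseline-change correlation is −√((1 − r)/2), so the residual SD is 12 × √((1 + r)/2), on 28 df.

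| r (assumed) | √((1 + r)/2) | Mean half-width, no-baseline MMRM | Mean half-width, ANCOVA | Disagree on significance, true change 4 |
|---|---|---|---|---|
| 0.3 | 0.81 | 4.44 | 3.59 | 15.1% |
| 0.5 | 0.87 | 4.44 | 3.85 | 10.5% |
| 0.7 | 0.92 | 4.44 | 4.10 | 6.2% |

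Half-widths and disagreement rates are from simulation at n = 30, with at least 100,000 trials per row.

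**One worked data set.** Take n = 30, observed mean change 4.2, observed SD 12 and observed baseline-change correlation −0.5.
- No-baseline MMRM: t = 4.2/2.191 = 1.917, 29 df, p = 0.065.
- ANCOVA: SE = 12 × √(0.75 × 29/28)/√30 = 1.931; t = 4.2/1.931 = 2.175, 28 df, p = 0.038.

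**When the gap closes.** If baseline is uncorrelated with change, the two disagree in only 1.4% of trials at a true change of 4.

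**The MMRM with baseline (SAP 6.10.5).** With one post-baseline visit, a model containing baseline and a one-level visit factor is the ANCOVA: same estimate, same SE, no disagreement. The figures in the table therefore apply only to the version in 6.1 and 6.2.

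**The borrowed models.** ICR, ISF and DIA have post-baseline values at Visits 4 to 14 (SAP Table ITSZ.6.2), and vital signs at Visits 7, 11 and 14. An MMRM is the right class of model under the 6.1 rule. What is undetermined is the baseline term. No size is given here, because the documents provide no SD or correlation for these variables.

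**The case against.** The strongest reply is that the SAP does settle the primary model. The 6.1 rule, together with CGM outcomes at two visits only, puts time in range under ANCOVA. SAP 6.3, 6.9.1 and 6.13 and Protocol 9.4.2 all say the same. SAP 6.2 sends the reader to 6.9, where the primary analysis is ANCOVA alone. The Protocol's amendment history records that ANCOVA replaced the previous method because CGM data are derived only for Visits 3 and 14. That stands. A reader might infer that nothing ranks the two models, or that the sponsor is free to choose between them after seeing the data. The documents do not support this: anyone citing the MMRM would contradict several sections of a SAP that says it was approved before any participant received study drug.

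A reader might also infer that having two primary models raises the type I error to about 7% to 11%. It does not. Under no change, simulation gives rejection by at least one model in 11.0%/8.7%/6.8% of trials at r = 0.3/0.5/0.7, and by ANCOVA alone in the same 11.0%/8.7%/6.8%. The excess arises because the ANCOVA standard error of the LS mean treats the sample mean baseline as fixed. That is a separate issue, and tidying the model wording would leave it unchanged.

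Finally, the study is an exploratory pilot, is not formally powered, and has no decision rule tied to primary significance. This limits the severity. None of it resolves the incorrect MMRM sentences or the contradictory model for ICR, ISF, DIA and vital signs.

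**Conclusion.** The point holds as a specification error of minor to moderate weight. Three current passages attach an MMRM to an endpoint that the rest of both documents assigns to ANCOVA. Read literally in the no-baseline form, they would widen the mean 95% CI half-width from 3.59/3.85/4.10 to 4.44 points and change the significance call in about 15%/10%/6% of trials at a true change of 4 points. These sizes rest on n = 30, the plan's SD of 12, equal variances and assumed correlations of 0.3/0.5/0.7. They also depend on placing the true change near the significance boundary, and they vanish if the MMRM includes baseline. They affect the reported p-value and interval, not a confirmatory decision.

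The part that intent does not resolve is the set of borrowed models: for ICR, ISF, DIA and vital signs the SAP describes the reference MMRM both with and without baseline.

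**What to change.** - State one primary model and contrast everywhere: mean change from Visit 3 to Visit 14 in percentage of time in 70 to 180 mg/dL, by the ANCOVA of SAP 6.9.1 and Protocol 9.4.2, two-sided 0.05.
- Remove the reference to the primary efficacy endpoint from the MMRM sentences in SAP 6.1, SAP 6.2 and Protocol 9.4.1.
- In SAP 6.9.2, 6.9.3 and 6.10.5, replace the likeness to the primary endpoint with one explicit MMRM: baseline value, visit, and the within-patient covariance structure.
- If a paired-change analysis of time in range is kept, label it a sensitivity analysis.

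The cost is wording in five SAP sections and one sentence in the Protocol. No new data, participants or analyses are needed.
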